As shown in Figure 3, proposed is a 2X2 factorial randomized clinical effectiveness trial testing the effects of combining CM as an adjunct to state-of-the-art, evidence-based CBT (CBT + CM vs. CBT only) and the effects of a single, long-term incentive for bioverified abstinence/no heavy drinking at 6-months follow-up (Long Term Incentive vs. No Incentive). All patients will be referred to standard aftercare and encouraged to participate in 12-step programs following the intervention. Use of aftercare and other health care utilization will be collected based on objective measures (VA electronic medical record) and participant report. Health-related quality of life will be collected at each follow-up. The primary endpoint (AIM 1) will be number of heavy drinking days in the past 30 days at the 6-month follow-up. Cost effectiveness analysis (AIM 2) will be performed using quality-adjusted life years (QALY) as the outcome. The utility of a long-term incentive (AIM 3) will be tested by examining use of aftercare and other alcohol-related treatment and heavy drinking days in the past 30 days at the 6 and 12-month follow-ups.

D.2. Patient Identification, Eligibility, and Recruitment

Patients will be identified from the Durham VA Health Care System (DVAHCS) using the hospital's computerized medical record. Records will be screened for AUD. After mailing introductory materials with an opt-out number, we will contact those who do not opt out via telephone to explain the study and recruit them for participation. If necessary, in order to reach female veterans, we can oversample women for the screening mailouts.

Figure 3. Trial Design

We will also utilize reactive recruitment methods as needed to reach potentially eligible veterans. For example, we will seek referrals from the DVAHCS Substance Use Disorders Clinic. In order to reach female veterans, we will seek referrals from the Women's Health Clinic. In addition, we will post IRB-approved flyers and brochures throughout the DVAHCS catchment area, especially in clinic areas and Vet Centers. In addition, we will post, if necessary, flyers and brochures in the community, in local restaurants, laundromats, university student centers, etc. We will also use online classified advertisements such as Craigslist.com to reach potential participants.

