D.8.9. Quality of Life and Health Care Utilization. VA administrative data will be accessed via the VA Corporate Data Warehouse to provide objective measures of VA health care utilization. Our team has extensive experience accessing and utilizing VA data (Elhai, [name], & Ford, 2008; [name], Bosworth, Grambow, Dudley, & [name], 2002; [name], Bosworth, Stechuchak, Strauss, & Butterfield, 2006). Additionally, we will collect self-reported use of non-VA healthcare and 12-step programs and information about insurance coverage. Health care related quality of life will be assessed with the EuroQol (United Kingdom Alcohol Treatment Trial Team, 2005) at baseline and each of the follow-ups.

D.9. Participant Reimbursement

Participants will be paid as follows:

Project Milestone	Amount
Screening visit	\$50
CM abstinence reinforcement	\$611
End-of-treatment visit	\$50
6-month follow-up	\$100
Bioverified abstinence at 6 month follow-up (if randomized to long-term incentive condition)	\$300
12-month follow-up	\$125
TOTAL	\$1236

D.10. Potential Challenges and Solutions

One potential challenge to the success of this project is recruitment and retention. Previous AUD trials in veterans indicate lost-to-follow-up rates near 30% at 12 month follow-up (Hagedorn et al., 2013). We have implemented several methods to increase retention in our trials (e.g., pre-alert letters, birthday cards, reminder

calls, thank you notes) and have obtained excellent retention rates ($>80\%$ at 12-months) in substance using populations (e.g., homeless veterans). We will use these methods and have budgeted to provide an incentive to participants to complete each follow-up. Missing data will be treated as indicative of relapse/heavy drinking. Our pilot data and experience in previous trials indicate that proactive recruitment of veterans with AUD is feasible. To augment our proactive recruitment method, we could include reactive recruitment strategies and include referrals from the SUD clinic at DVHCS. Another potential concern is lost/stolen study equipment. We now have extensive experience with providing veterans with a smartphone and monitoring devices to perform mobile monitoring for CM (e.g., R34AA023877; R01CA196304; 1I01HX001109; 1I01RX001301) and have budgeted for anticipated lost/stolen equipment. Costs of lost equipment will be captured and included in cost analyses.

E. DATA AND SAFETY MONITORING

E.1. Risk/Benefit Ratio

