We plan to ask participants to report both gender and biological sex so that we can evaluate the role of biological sex on study outcomes. The association between sex and outcomes will be evaluated for all three aims. We will conduct sensitivity analyses to determine how variability in demographic/baseline variables influence estimates of treatment effects by analyzing and reporting the effects of randomization on males and females separately.

Multilevel modeling (MLM) will be used to analyze primary treatment outcomes (i.e., number of heavy drinking days; abstinence outcomes). MLM is appropriate for analyzing repeated-measures data; however, unlike ANOVA, MLM can accommodate data missing at random (Searle, Casella, & McCulloch, 1992). Because MLM takes into account the shared variance among observations within a given person, it can be used to leverage repeated measurements of alcohol use to enhance statistical power.

Although we do not anticipate much missing baseline data, we do anticipate missing values at post-treatment and each of the 6- and 12-month follow-ups due to attrition. Given evidence that maximum likelihood (ML) and multiple imputation (MI) provide the least biased results in comparison to last observation carried forward and worst-case scenario (i.e., missing=relapsed) in alcohol clinical trials under varying missing data assumptions (Hallgren & Witkiewitz, 2013), both approaches will be used here. MLM uses ML estimation; thus, missing values result in casewise—but not listwise—deletion. Consequently, participants with missing data will still be included in the analyses; estimates based on them will simply have a greater level of uncertainty. MI will be used to impute missing data using baseline demographic, clinical, and drinking measures. Regression parameter estimates will be computed for each imputation dataset and then pooled using Rubin's rules (Rubin, 1976). Sensitivity analyses will be conducted to determine how modeled treatment effects may vary by missing-data approach.

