Aim 1: To examine the first hypothesis that CM will be associated with greater treatment engagement and treatment completion than the control condition, treatment engagement will be defined as the number of counseling sessions completed, with treatment completion defined as completion of all 12 counseling sessions. Potential group differences in treatment engagement as a function of counseling sessions completed will be examined using independent *t*-tests. Contingency-table analysis will be used to examine whether a greater proportion of the CM participants complete the treatment in comparison to the control group. The second hypothesis is that CM will be associated with higher rates of self-reported abstinence and fewer heavy drinking days at 6 and 12 months. MLM will be used to model each of these outcomes. Specifically, logistic MLM will be

conducted to model abstinence as a function of treatment, time (categorized as end of treatment, 6 months, 12 months), and the interaction between treatment and time. Randomization to long-term abstinence incentive will be covaried. Linear contrasts will be specified at each time point to examine the hypothesis that CM will result in higher abstinence rates than CBT alone at 6 and 12 months. A similar count-based model (e.g., Poisson, negative binomial) will be conducted to analyze number of days of heavy drinking (per 30 days). In addition to modeling the effects of treatment, time, and the interaction between treatment and time, number of days of heavy drinking recorded at baseline and randomization to the long-term abstinence incentive will be covaried. Again, linear contrasts will be derived at each time point to compare treatment effects at 6 and 12 months.

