Power calculations provided below were performed with Power Analysis and Sample Size software (PASS, Version 12: NCSS LLC, Kaysville, Utah). The sample size estimate is based on the first hypothesis that the CM intervention will result in higher overall self-reported abstinence rates and fewer days of heavy drinking at 6-months post-randomization. As described in the analysis section, this hypothesis will be tested via linear contrasts specified within the context of MLM analyses. Because this will be tested using repeated-measures data, statistical power will depend on the effective sample size (ESS). The ESS is the number of statistically independent observations available for this study, which is equivalent to the total number of observations (number of participants x number of data collections) adjusted for within-individual correlations. As the intraindividual, or intra-class, correlation (ICC) decreases, the ESS increases. Given that we found an ICC of .20 for 7-day point prevalence measured at posttreatment, 3 months, and 6 months in an RCT with 218 smokers featuring CM as the experimental treatment (R01 CA196304), we anticipate a similar, if not smaller, figure in this trial, given longer intervals between observations. Using this ICC value, with 140 participants with up to 3 observations each, the ESS would be 300. Even with an unexpectedly high 15% attrition at each observation point, such that only 119 complete treatment, 101 6-month follow-up, and 86 12-month follow-up, the ESS for examining linear contrasts would be 227, which would be sufficient to detect treatment effects as small as Cohen's $d = 0.43$ with 90% power. Because the previous trial examining the effect of CM as an adjunct to behavioral treatment found large effects (Cohen's $d = 0.92$; McDonell et al., 2017) on heavy drinking days, our proposed sample size has sufficient statistical power.

G. PROJECT MANAGEMENT PLAN and TIMELINE

The scheduled project timeline is illustrated in Table 5. Members of this multi-disciplinary research team have experience in one or more key components of the

Activity	Year 1				Year 2				Year 3				Year 4				Year 5			
	1	2	3	4	1	2	3	4	1	2	3	4	1	2	3	4	1	2	3	4
Hire/Train Staff	■																			
Recruitment		■	■	■	■	■	■	■	■	■	■	■								
Intervention			■	■	■	■	■	■	■	■	■	■								
Follow-ups: post-txt, 6-and 12-months			■	■	■	■	■	■	■	■	■	■		■	■	■	■			
Data Analysis														■	■	■	■	■	■	■

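### Section D.10 scores missing data as heavy drinking while Section F uses maximum likelihood and multiple imputation; the two are never reconciled, and the imputation sentence does not name randomised arm

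*Combined protocol and SAP*

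**What the plan says.** Three places bear on missing outcomes.

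- **Section D.10 (Potential Challenges and Solutions)**, in its discussion of retention: "Missing data will be treated as indicative of relapse/heavy drinking". It names no outcome, gives no value to enter and does not say whether the rule is primary or a sensitivity analysis.
- **Section F, missing-data paragraph**: it cites a published comparison of methods, with this conclusion: "maximum likelihood (ML) and multiple imputation (MI) provide the least biased results in comparison to last observation carried forward and worst-case scenario (i.e., missing=relapsed". The plan is to use both ML and MI. Participants with missing visits stay in the multilevel model with nothing filled in. For imputation, "MI will be used to impute missing data using baseline demographic, clinical, and drinking measures". It closes with "Sensitivity analyses will be conducted to determine how modeled treatment effects may vary by missing-data approach", without listing the approaches or mentioning D.10. It does not say whether ML or MI is primary.
- **Section F, power paragraph**: the effective sample size (ESS) is reduced for lost visits, from 300 to 227.

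The endpoint concerned is set in Section D.1: "The primary endpoint (AIM 1) will be number of heavy drinking days in the past 30 days at the 6-month follow-up". The Aim 1 analysis text fits it with treatment, time and their interaction: "A similar count-based model (e.g., Poisson, negative binomial) will be conducted to analyze number of days of heavy drinking (per 30 days".

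**The concern.** The two rules cannot both govern one analysis. ML leaves a missing visit empty; D.10 fills it. Section F itself names the D.10 rule as the inferior comparator.

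If D.10 were followed, the primary result would depend on a number that the plan never states. Relapse or heavy drinking is a status, and the endpoint is a count from 0 to 30, so the analyst would have to choose the value, possibly after seeing the data. With equal retention the rule dilutes a real effect on the risk-difference or count scale. With unequal retention it scores a difference in attendance as a difference in drinking.

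The imputation sentence raises a separate problem. If arm is absent from the imputation model, missing values are drawn as though the arms did not differ, and the estimate moves toward no effect. The planned comparison of missing-data approaches would then show a gap between ML and MI that comes from the imputation model and says nothing about the missing-data assumption.

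**Working it through.** **1. The plan's own figures.** Attrition of 15% per visit gives 140 × 0.85 = 119, × 0.85 = 101 and × 0.85 = 86 observed. Missing at 6 months: 140 − 101 = 39 (27.9%). Missing at 12 months: 140 − 86 = 54 (38.6%). With ICC 0.20, a participant with m visits contributes m / (1 + (m − 1) × 0.20).

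- No attrition: 140 × 3 / 1.4 = 300.
- With attrition, 86 people have three visits, 15 have two and 18 have one: 86 × 3/1.4 + 15 × 2/1.2 + 18 = 227.3.
- At a total of 227 and d = 0.43, two-sided alpha 0.05 (assumed; not stated in the plan) gives power 0.8996.

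All three stated figures reproduce. The 227 counts observed visits only. That fits ML and does not fit D.10, under which no visit would be missing.

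**2. Effect of each rule when retention is equal.** Loss levels: 20% (the team's reported 12-month retention above 80%, D.10), 30% ("Previous AUD trials in veterans indicate lost-to-follow-up rates near 30% at 12 month follow-up", D.10), and 27.9% and 38.6% from the power paragraph. A 10% row is added as an assumption, because the primary endpoint is at 6 months and the 20% and 30% figures are for 12 months. Let r be the share retained.

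- Abstinence under D.10: gap = 20 points × r (the 20 points are assumed).
- Count under D.10, k days entered, assumed true means 8 and 5 (rate ratio 0.625): RR = (5r + k(1 − r)) / (8r + k(1 − r)).
- MI without arm: d = 0.43 × r. For the count, missing values centre on the pooled mean 6.5, so k = 6.5 in the same formula.

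| Missing | Abstinence gap, D.10 | RR, k=1 | RR, k=5 | RR, k=15 | RR, k=30 | d, MI without arm | RR, MI without arm |
|---|---|---|---|---|---|---|---|
| 10% | 18.0 | 0.63 | 0.65 | 0.69 | 0.74 | 0.39 | 0.66 |
| 20% | 16.0 | 0.64 | 0.68 | 0.74 | 0.81 | 0.34 | 0.69 |
| 27.9% | 14.4 | 0.64 | 0.70 | 0.78 | 0.85 | 0.31 | 0.71 |
| 30% | 14.0 | 0.64 | 0.70 | 0.79 | 0.86 | 0.30 | 0.72 |
| 38.6% | 12.3 | 0.65 | 0.73 | 0.83 | 0.89 | 0.26 | 0.75 |

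Example, 27.9% and k = 15: (3.607 + 4.179) / (5.771 + 4.179) = 7.79 / 9.95 = 0.78.

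**3. D.10 with unequal retention and no true effect** (all splits assumed).

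- Count: 70 per arm, observed mean 5 to 10 days in both arms, the 39 missing split 15 CM and 24 control. The false difference favouring CM is (24 − 15)/70 × (k − mean). It is 2.6 to 3.2 days for k = 30, 0.6 to 1.3 for k = 15, and −0.5 to −1.2 for k = 1. The sign depends on k.
- Abstinence: 40% in both arms, retention 77% and 67%. The false gap is (0.77 − 0.67) × 0.40 = 4 points.

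**4. Simulation checks at the power section's attrition.**

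- Single 6-month continuous outcome, true d 0.43, baseline correlation 0.5, missing completely at random, 10 imputations, 2,000 runs: MI without arm 0.309, with arm 0.432.
- Three continuous visits, ICC 0.20, dropout depending on baseline, 200 runs, estimates at 6 and 12 months: ML mixed model 0.418 and 0.415 (Monte Carlo error 0.013 to 0.015); MI without arm 0.298 and 0.253; MI with arm 0.413 and 0.411.
- Three overdispersed counts, missing completely at random, predictive mean matching, 10 imputations, 400 runs, true rate ratio 0.625: without arm 0.720 and 0.755; with arm 0.632 and 0.636; with arm and earlier visits 0.635 and 0.641.

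**The case against.** The strongest reply is that the documents already show which rule governs. D.10 deals with recruitment, retention and lost equipment. Section F is the statistical section; it argues against scoring missing as relapsed and reduces the ESS for lost visits. The final sentence of the missing-data paragraph could also accommodate D.10 as a sensitivity analysis. This stands as a reading of intent, and it is why ML is taken here as the likely primary method. It does not remove an unqualified contrary sentence, and no text gives D.10 a sensitivity role.

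On imputation, the sentence does not say that only baseline measures will be used, and many analysts would include arm by habit. That also stands: the defect is an omission in the text and does not prove that arm will be left out.

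Several objections limit the size:

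- Abstinence will be modelled on the logistic scale, where dilution can be smaller. At 27.9% loss, 40% v 20% goes from an odds ratio of 2.67 to 2.41, and 60% v 40% from 2.25 to 1.88 (base rates assumed). The risk ratio is unchanged when retention is equal.
- Entering 1 day hardly moves the rate ratio.
- The power section calls its own attrition high: "Even with an unexpectedly high 15% attrition at each observation point".
- The 77% v 67% retention split has no source in the documents. Hypothesis 1a concerns treatment engagement and completion, which are not follow-up attendance.
- D.10 is not biased for abstinence if those missing are in fact drinking. For the count, the value entered must also be right.

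These points narrow the illustrations. They leave the contradiction and the unnamed arm in place.

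**Conclusion.** The concern holds and should be fixed. D.10 and Section F give incompatible rules. D.10 cannot be applied to the primary count without a value the plan does not supply, and it conflicts with the basis of the plan's own power calculation. MI run as listed attenuates the arm effect by about the missing fraction: from 0.43 to about 0.31 at 6 months and 0.26 at 12 months under the power section's attrition, and to about 0.39 if only 10% are missing.

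The text findings rest on no assumption. The sizes depend on the assumed day means, abstinence gap and retention patterns, and the MI sizes on reading its variable list as complete. The problem is confined to the D.10 sentence and the MI branch. The ML multilevel model showed no material bias under the missing-at-random dropout simulated.

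**What to change.** 1. In Section F, state that the ML multilevel model is the primary analysis of heavy drinking days and abstinence, with MI supportive. Delete the D.10 sentence, or replace it with: *As a sensitivity analysis for binary abstinence only, missing follow-ups will be counted as not abstinent.* If a similar sensitivity analysis is wanted for the count, fix the day values to be entered in advance.
2. Reword the MI sentence so that the imputation model contains both randomised factors (CM and long-term incentive), the randomisation stratum (comorbid non-tobacco SUD), the baseline demographic, clinical and drinking measures, and all observed post-treatment, 6-month and 12-month drinking outcomes. Naming arm removes the attenuation. Adding the follow-up outcomes changed the simulated rate ratio by less than 0.01, but it lets MI use the same drinking data as the ML model.

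The cost is two sentences and slightly more analysis work. No new data are needed.
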